7.3.4 QuantiFERON test/or T-Spot test

At the discretion of the investigator, a QuantiFERON Gold®TM ([11](#)) test /or T-Spot test ([11](#)) conducted in local lab may be substituted for the PPD skin test. A description of the QuantiFERON Gold test follows: “This Enzyme-linked Immunosorbent Assay (ELISA) test detects the release of Interferon-gamma (IFN- γ) in fresh heparinized whole blood from sensitized persons when it is incubated with mixtures of synthetic peptides simulating two proteins present in *M. tuberculosis*: Early Secretory Antigenic Target-6 (ESAT-6) and Culture Filtrate Protein-10 (CFP-10). ESAT-6 and CFP-10 are secreted by all *M. tuberculosis* and pathogenic *M. bovis* strains. Because these proteins are absent from all Bacille Calmette-Guérin (BCG) vaccine strains and from commonly encountered Non Tuberculous Mycobacteria (NTM) except *M. kansasii*, *M. szulgai*, and *M. marinum*, QFT-G is expected to be more specific for *M. tuberculosis* than tests that use tuberculin Purified Protein Derivative (PPD) as the antigen”.

T-Spot is another IFN- γ release assays in diagnosing *M. tuberculosis* infection. For this test, peripheral blood mononuclear cells (PBMCs) are incubated with two mixtures of peptides, one representing ESAT-6 and the other representing CFP-10. The test uses an enzyme-linked immunospot assay (ELISpot) to detect increases in the number of cells that secrete IFN- γ .

In the situation QFT-G or T-Spot is unavailable by local testing, incubated whole blood sample could be sent to central lab for QFT-G testing. If QFT-G/or T-Spot result is indeterminate, a retest is required at earliest to determine the eligibility of the subject. If retest is indeterminate or positive, the subject should be screen failed. If retest is negative, the PI should assess the subject's clinical condition and decide if the subject could be included.

7.3.5 Clinical Laboratory Testing

Routine, non-fasting clinical laboratory (hematology and chemistry and urinalysis) tests will be performed as detailed in [Section 5.12 –Time and Event Table](#). At the discretion of the investigator, additional samples may be taken for safety reasons. All blood samples will be measured at a designated central laboratory.

A urine pregnancy test will be performed for all females of child bearing potential as detailed in [Table 3](#).

The study clinical laboratory tests including analytes for clinical chemistry and hematology are shown below in [Table 3](#).

Table 3. Clinical Laboratory Testing Lists

CHEMISTRY	HEMATOLOGY	Urinalysis	OTHER
Albumin	Haemoglobin	pH	Hepatitis B surface antigen ¹
Alkaline phosphatase	Haematocrit	Protein	Hepatitis C virus antibody ¹
Alanine amino-transferase (ALT or SGPT)	Platelet count	Glucose	HIV test ¹
Aspartate amino-transferase (AST or SGOT)	WBC count	Bilirubin and White Cell Count	Urine pregnancy test (in clinic) ²
Bilirubin, direct	RBC count		FSH ³
Bilirubin, indirect	Neutrophils, absolute		β -HCG blood test ⁴
Bilirubin, total	Neutrophils, segs (%)		Lipid Profile ⁵ (fasting): Total Cholesterol, Low Density Lipoprotein (LDL) High Density Lipoprotein (HDL) Triglycerides
Calcium	Neutrophils, bands (%)		Stool culture /microscopy for: Salmonella, Shigella, Campylobacter, Fecal Ova and Parasites
Chloride	Basophils (%)		Clostridium difficile toxin
CO ₂ content/Bicarbonate	Eosinophils (%)		Fecal calprotectin ⁶
Creatinine	Eosinophils , absolute		Thyroid Function Test, including TSH, free T4 and free T3.
Creatine phosphokinase (CPK), total	Lymphocytes (%)		PK sampling ⁷
Gamma glutamyl transferase (GGT)	Monocytes (%)		CRP
Glucose			
Phosphorus			
Potassium			
Protein, total serum			
Sodium			
Urea nitrogen (BUN)			
Uric Acid			

1 Assessed at Visit 1 (Screening) only

2 all visits subsequent to the screening visit

3 FSH to confirm postmenopausal status at screening visit only

4 Only for females of child-bearing potential at screening, and if urine pregnancy test positive

5 fasting lipid profile will be done as per [Section 5.12 Time and Eventtable](#).

6 for biomarker assessment

7 Only done as per [Section 7.4 Pharmacokinetics](#)

7.3.6 C-Reactive Protein (CRP)

C-reactive protein is considered an acute-phase protein which provides an objective criterion of inflammatory activity. CRP has a short half-life (19 hours) and therefore rises early after the onset of inflammation and rapidly decreases after resolution of the inflammation (12). It is induced by interleukin-6, TNF- α and other proinflammatory cytokines that are produced

within the intestinal lamina propria. CRP measurements will be collected at screening, baseline, Week 1, 4, 8, 9, 12, 16 and 18 and will be analyzed by a central laboratory.

7.3.7 Fecal Calprotectin

Fecal calprotectin is a 36kDa calcium and zinc binding protein which is neutrophil derived and it represents 60% of cytosolic proteins in granulocytes. It is considered as a measurement of neutrophil migration to the gastrointestinal tract. Fecal calprotectin is a very stable marker (stable for one week at room temperature). There is a growing body of evidence that fecal calprotectin correlates well with disease activity and making it a useful tool in monitoring disease and treatment (13). Fecal calprotectin measurement will be collected as detailed in [Section 5.12 – Time and Event table](#), from screening until the end of study visit (week 18) and will be analyzed by a central laboratory.

Subjects will be supplied with stool sample collection kits in advance and will be instructed to collect the sample at home, 1 day before the upcoming visit at which they have to provide the sample. Fecal samples (~20 g) for analysis of fecal calprotectin will be collected into the labeled stool collection containers, at protocol specified times (see [Section 5.12 – Time and Event table](#)) and shipped to central laboratory based on the laboratory manual. Samples will be analyzed using a validated analytical method.

7.3.8 Lipid Profile Testing

A fasting lipid profile blood collection, as per [Section 5.12 – Time and Event table](#), will require subjects to refrain from all food and liquids (water and non-study medications permitted) for at least 10 hours prior to scheduled laboratory tests.

7.3.9 Liver Chemistry – Stopping and Follow-up Criteria

Phase II liver chemistry stopping and follow up criteria have been designed to assure subject safety and evaluate liver event etiology (in alignment with the FDA premarketing clinical liver safety guidance).

Phase II liver chemistry stopping criteria 1-5 are defined below:

1. ALT $\geq 3 \times \text{ULN}$ **and** bilirubin $\geq 2 \times \text{ULN}$ ($>35\%$ direct bilirubin) (or ALT $\geq 3 \times \text{ULN}$ **and** INR >1.5 , if INR measured).

NOTE: if serum bilirubin fractionation is not immediately available, study drug should be discontinued if ALT $\geq 3 \times \text{ULN}$ **and** bilirubin $\geq 2 \times \text{ULN}$. Serum bilirubin fractionation should be performed if testing is available. If testing is unavailable, **record presence of detectable urinary bilirubin on dipstick**, indicating direct bilirubin elevations and suggesting liver injury.

2. ALT $\geq 5 \times \text{ULN}$.

3. ALT \geq 3xULN if associated with the appearance or worsening of symptoms of hepatitis or hypersensitivity such as fatigue, nausea, vomiting, right upper quadrant pain or tenderness, fever, rash or eosinophilia.
4. ALT \geq 3xULN persists for \geq 4 weeks.
5. ALT \geq 3xULN and cannot be monitored weekly for 4 weeks

When any of the liver chemistry stopping criteria 1-5 is met, do the following:

- **Immediately** withdraw investigational product.
- Report the event to Reistone/designated CRO **within 24 hours** of learning its occurrence.
- Complete the liver event eCRF and SAE data collection tool if the event also meets the criteria for an SAE. All events of ALT \geq 3xULN **and** bilirubin \geq 2xULN ($>35\%$ direct bilirubin) (or ALT \geq 3xULN **and** INR >1.5 , if INR measured; INR measurement is not required and the threshold value stated will not apply to patients receiving anticoagulants), termed 'Hy's Law', **must be reported as an SAE (excluding studies of hepatic impairment or cirrhosis)**.

NOTE: if serum bilirubin fractionation is not immediately available, study drug should be discontinued if ALT \geq 3xULN **and** bilirubin \geq 2xULN. Serum bilirubin fractionation should be performed if testing is available. If testing is unavailable, **record presence of detectable urinary bilirubin on dipstick**, indicating direct bilirubin elevations and suggesting liver injury.

- Complete the liver imaging and/or liver biopsy eCRFs if these tests are performed
- Perform liver event follow up assessments, and monitor the subject until liver chemistries resolve, stabilize, or return to baseline values as described below.
- Withdraw the subject from the **study** (unless further safety follow up is required) after completion of the liver chemistry monitoring as described below.
- Do not re-challenge with investigational product.

In addition, for criterion 1:

- Make every reasonable attempt to have subjects return to clinic within **24 hours** for repeat liver chemistries, liver event follow-up assessments (see below), and close monitoring.
- A specialist or hepatology consultation is recommended.

- Monitor subjects twice weekly until liver chemistries (ALT, AST, alkaline phosphatase, bilirubin) resolve, stabilise or return to within baseline values

For criteria 2, 3, 4 and 5:

- Make every reasonable attempt to have subjects return to clinic **within 24-72 hrs** for repeat liver chemistries and liver event follow up assessments (see below)
- Monitor subjects weekly until liver chemistries (ALT, AST, alkaline phosphatase, bilirubin) resolve, stabilize or return to within baseline values; criterion 5 subjects should be monitored as frequently as possible.

Subjects with $\text{ALT} \geq 3 \times \text{ULN}$ **but** $< 5 \times \text{ULN}$ **and** bilirubin $< 2 \times \text{ULN}$, without hepatitis symptoms or rash, and who can be monitored weekly for 4 weeks:

- Notify the Reistone/designated CRO medical monitor within 24 hours of learning of the abnormality to discuss subject safety.
- Can continue investigational product.
- Must return weekly for repeat liver chemistries (ALT, AST, alkaline phosphatase, bilirubin) until they resolve, stabilise or return to within baseline.
- If at any time these subjects meet the liver chemistry stopping criteria, proceed as described above.
- If, after 4 weeks of monitoring, $\text{ALT} < 3 \times \text{ULN}$ and bilirubin $< 2 \times \text{ULN}$, monitor subjects twice monthly until liver chemistries normalize or return to within baseline values.

For criteria 1-5, make every attempt to carry out the **liver event follow up assessments** described below:

- Viral hepatitis serology including:
 - Hepatitis A IgM antibody;
 - Hepatitis B surface antigen and Hepatitis B Core Antibody (IgM);
 - Hepatitis C RNA;
 - Cytomegalovirus IgM antibody;
 - Epstein-Barr viral capsid antigen IgM antibody (or if unavailable, obtain heterophile antibody or monospot testing);
 - Hepatitis E IgM antibody
- Blood sample for pharmacokinetic (PK) analysis, obtained within 24 hours of last dose. Record the date/time of the PK blood sample draw and the date/time of the last dose of investigational product prior to blood sample draw on the eCRF. If the date or time of the

last dose is unclear, provide the subject's best approximation. If the date/time of the last dose cannot be approximated OR a PK sample cannot be collected in the time period indicated above, do not obtain a PK sample. Instructions for sample handling and shipping are in the SPM.

- Serum creatine phosphokinase (CPK) and lactate dehydrogenase (LDH).
- Fractionate bilirubin, if total bilirubin $\geq 2 \times \text{ULN}$.
- Obtain complete blood count with differential to assess eosinophilia.
- Record the appearance or worsening of clinical symptoms of hepatitis, or hypersensitivity, such as fatigue, nausea, vomiting, right upper quadrant pain or tenderness, fever rash or eosinophilia as relevant on the AE report form.
- Record use of concomitant medications, acetaminophen, herbal remedies, other over the counter medications, or putative hepatotoxins, on the concomitant medications report form.
- Record alcohol use on the liver event alcohol intake eCRF.

The following are required for subjects with ALT $\geq 3 \times \text{ULN}$ and bilirubin $\geq 2 \times \text{ULN}$ ($> 35\%$ direct) but are optional for other abnormal liver chemistries:

- Anti-nuclear antibody, anti-smooth muscle antibody, and Type 1 anti-liver kidney microsomal antibodies.
- Liver imaging (ultrasound, magnetic resonance, or computerized tomography) to evaluate liver disease.

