6.1.2 Study Drug Administration

Study medication will be self-administered by the subject twice daily, one (2 tablets) in the morning, another (2 tablets) in the afternoon. Approximately 8 - 12 hours between the morning and afternoon doses.

However, at baseline (Day 0) the first dose will be taken in the clinic. At Week 4 and at the end of treatment (Week 8) subjects should take their morning oral dose at the clinic. Study medication may be taken with or without food.

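### For liver stopping criteria 2–5, Section 7.3.9 schedules the follow-up visit at 24–72 hours but permits the PK sample only within 24 hours of the last dose

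*Protocol*

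**What the plan says.** All the relevant rules stand in Protocol Section 7.3.9 and apply once any of liver stopping criteria 1–5 is met.

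- Study drug: "Immediately withdraw investigational product".
- Scope of the assessments: "For criteria 1-5, make every attempt to carry out the liver event follow up assessments". The PK sample is one of them.
- Return visit, criterion 1: "Make every reasonable attempt to have subjects return to clinic within 24 hours for repeat liver chemistries". The follow-up assessments belong to this visit too.
- Return visit, criteria 2–5: "Make every reasonable attempt to have subjects return to clinic within 24-72 hrs for repeat liver chemistries and liver event follow up assessments".
- PK window: "Blood sample for pharmacokinetic (PK) analysis, obtained within 24 hours of last dose".
- Missed window: if "a PK sample cannot be collected in the time period indicated above, do not obtain a PK sample".

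The section does not say when the return-visit clock starts. It does require the date and time of both the last dose and the draw to be recorded. On dosing, Section 6.1.2 gives "Approximately 8 - 12 hours between the morning and afternoon doses", and all arms take tablets twice daily.

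**The concern.** Dosing has already stopped when the return clock for criteria 2–5 is running. A visit 24 to 72 hours later is therefore at or beyond the limit for the PK sample, and the missed-window rule then bars the draw. The section asks sites to make every attempt at an assessment that its own timetable rules out for four of the five criteria.

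What is at stake is modest. Section 7.3.9 says the criteria are there partly to establish the cause of a liver event, and a concentration near the event is one of the few listed items that bears on drug exposure. Exposure-response is also a secondary objective (Section 3.2). Under the present timing, the criteria 2–5 events that do yield a concentration would be those where the subject happened to return early.

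**Working it through.** The plan gives no figure to reproduce. The check is whether the stated time windows can overlap.

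**Inputs from the documents**
- Sample allowed only up to 24 h after the last dose (Section 7.3.9).
- Return at 24–72 h for criteria 2–5, and within 24 h for criterion 1 (Section 7.3.9).
- Gap between morning and afternoon doses, *g* = 8 to 12 h (Section 6.1.2), so the overnight gap is 24 − *g* = 12 to 16 h.

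**Assumptions**
- Drug is stopped at a random time of day.
- The return time is uniform over the stated window.

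**Set-up.** Let *u* be the time from the last dose to the stop of drug, and *t* the time from the stop to the return visit. The sample is allowed if *u* + *t* ≤ 24 h. If the return clock runs from the last dose instead, the condition is *t* ≤ 24 h.

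**Time already elapsed at the stop.** The stop falls in the daytime gap with probability *g*/24 and in the overnight gap otherwise, and is uniform within each. So E[*u*] = [*g*² + (24 − *g*)²]/48.
- *g* = 8: (64 + 256)/48 = 6.67 h, maximum 16 h.
- *g* = 12: (144 + 144)/48 = 6.00 h, maximum 12 h.

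**Criteria 2–5, literal 24–72 h.** Time since the last dose runs from 24 h up to 72 + 12 = 84 h or 72 + 16 = 88 h. The share allowed is 0% apart from a visit at exactly 24 h. Starting the clock at the last dose does not change this.

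**Criteria 2–5, read as any time up to 72 h.** Because *u* never exceeds 16 h, the share allowed is (24 − E[*u*])/72.
- *g* = 8: 17.33/72 = 24%.
- *g* = 12: 18/72 = 25%.
- Clock from the last dose: 24/72 = 33%.

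**Criterion 1, return within 24 h.** The share allowed is (24 − E[*u*])/24.
- *g* = 8: 17.33/24 = 72%.
- *g* = 12: 18/24 = 75%.
- Clock from the last dose: 24/24 = 100%.

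| Reading | Clock from stop of drug | Clock from last dose |
|---|---|---|
| Criteria 2–5, literal 24–72 h | 0% | 0% |
| Criteria 2–5, up to 72 h | 24–25% | 33% |
| Criterion 1, up to 24 h | 72–75% | 100% |

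**The case against.** **The missed window is foreseen.** The section says what to do when the sample cannot be drawn in time, and the assessments are best-effort. Sites can therefore follow the text without breaching it. That is true, but the fallback confirms the loss of the sample and does not prevent it.

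**The word 'within' may set only an upper limit.** Nothing bars a return before 24 hours, and Section 5.8 asks for early-withdrawal visits as soon as possible after drug is stopped. This is a fair reading, and it is why the lenient figures are shown. Even so, 67–76% of criteria 2–5 samples would be ruled out.

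**The sample could be drawn while the subject is still in clinic.** It could, if the criterion is recognised in time. But Section 7.3.5 has blood samples measured at a central laboratory, so the result need not be known before the subject leaves, and Section 7.3.9 ties the assessments to the return visit.

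**The 24-hour limit may keep concentrations measurable.** No visible passage gives this reason, and no half-life is visible against which to test it. The point neither supports nor refutes the limit.

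**The practical effect is small.** This stands. The SAP only lists liver event follow-up assessments (Section 16.7) and excludes PK analysis (Section 1), so no planned estimate is distorted. The expected number of liver events is not given, and one arm in four receives placebo for the first 8 weeks.

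**Conclusion.** The conflict is real and is confined to criteria 2–5. Taken literally, the return timing and the PK rule leave essentially no criteria 2–5 event with the listed sample. Under the lenient reading, about 24–33% of such events can have it. These percentages rest on a uniform return time and a stop at a random time of day under twice-daily dosing; the literal result needs neither assumption.

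A reader might infer two stronger conclusions that the documents do not support.

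- *That the sample will usually be barred across all liver events.* For criterion 1 it is usually feasible, and the mix of events by criterion is not given.
- *That the trial could not say whether liver events occur at high exposure.* Steady-state exposure is a secondary endpoint (Section 7.2.2), and Table 3 refers PK sampling to Section 7.4, which is redacted. Other concentrations from the same subjects may exist. The study procedures manual, cited for sample handling, is not available either.

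The primary analysis, sample size and type I error are not affected. This is a minor point, worth correcting because doing so is cheap.

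**What to change.** Reconcile the criteria 2–5 return-visit timing in Section 7.3.9 with the PK window and the do-not-obtain rule in the same section, so that the listed sample can be obtained for all five criteria. State when the return-visit clock starts. Which timing to change, and what the window should be, is for the sponsor to decide; the documents give no basis for choosing here.

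The cost is a minor text change to the protocol or study manual. If the sponsor chooses to allow later sampling, some concentrations may be below quantification. The dose and draw times already required would let them be read against time since dose.

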7.3.10 Pregnancy

If the subject is found to be pregnant, the subject must be withdrawn immediately, and any sponsor-supplied drug (SHR0302, placebo) should be immediately discontinued. In addition, any pregnancies in the partner of a male subject during the study, should also be recorded following authorization from the subject's partner. Any pregnancy that occurs after the first dose of investigational drug must be reported using a clinical trial pregnancy form. To ensure subject safety, each pregnancy must be reported to Reistone Biopharma/designated CRO within 24 hours of learning of its occurrence. The pregnancy must be followed up to determine outcome (including premature termination) and status of mother and the newborn should be followed up to 1 month after birth. Pregnancy complications and elective terminations for medical reasons must be reported as an AE or SAE. Pregnancies will remain blinded to the study team.

Should the pregnancy occur during or after administration of blinded drug, the investigator must inform the subject of their right to receive treatment information. If the subject chooses to

receive unblinded treatment information, the individual blind should be broken by the investigator. Subjects randomized to placebo need not be followed in the treatment phase.

If the female subject and/or female partner of a male subject agrees to the primary care physician being informed, the investigator should notify the primary care physician that the subject/female partner of the subject was participating in a clinical study at the time she became pregnant and provide details of treatment the subject received (blinded or unblinded, as applicable).

Spontaneous abortions must be reported as an SAE. Any SAE occurring in association with a pregnancy brought to the investigator's attention after the subject has completed the study and considered by the investigator as possibly related to the study treatment, must be promptly reported to Reistone Biopharma/designated CRO.

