7.3.14 AE and SAE reporting requirement and timeline

The investigator or site staff is responsible for detecting, documenting and reporting events that meet the definition of an AE or SAE. AEs will be collected from the start of study treatment (Visit 2) and until the follow up contact. SAEs will be collected from the time a subject consent to participate in the study up to and including any follow up contact.

All SAEs will be reported to Reistone Biopharma/designated CRO within 24 hours. Prompt notification of SAEs by the investigator to Reistone Biopharma/designated CRO is essential so that legal obligations and ethical responsibilities towards the safety of subjects are met. All SAEs will be followed up until resolution, until the condition stabilizes, until the event is otherwise explained, or until the subject is lost to follow-up. Once resolved, the SAE eCRF page will be updated. The investigator should report SAE/serious incident per local regulations and local EC requirement. The investigator will ensure that follow-up includes any supplemental investigations as may be indicated to elucidate the nature and/or causality of the SAE. This may include additional laboratory tests or investigations, histopathological examinations, or consultation with other health care professionals.

Reistone Biopharma/designated CRO has a legal responsibility to notify both the local regulatory authority and other regulatory agencies about the safety of a product under clinical investigation according to local regulations. Reistone Biopharma/designated CRO will comply with country specific regulatory requirements relating to safety reporting to the regulatory authority, Institutional Review Board (IRB)/Independent Ethics Committee (IEC) and investigators.

Investigator safety reports are prepared for suspected unexpected serious adverse reactions according to local regulatory requirements and Reistone Biopharma/designated CRO policy and are forwarded to investigators as necessary.

An investigator who receives an investigator safety report describing a SAE(s) or other specific safety information (e.g., summary or listing of SAEs) from Reistone Biopharma/designated CRO will file it with the IB and will notify the IRB/IEC, if appropriate according to local requirements.

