### **16.1.4 Serious Adverse Events (SAEs)**

A serious adverse event is any untoward medical occurrence that, at any dose:

- a. Results in death
- b. Is life-threatening
- c. Requires hospitalization or prolongation of existing hospitalization
- d. Results in disability/incapacity, or
- e. Is a congenital anomaly/birth defect

Document: \\ieedc-vnasc01\Biosdata\Reistone\SHR0302\CZA55021\Biostatistics

Author: [REDACTED]

Version Number:

Final v1.2

Version Date:

23Mar2021

Template No: CS\_TP\_BS016 Revision 5

Effective Date: 01Apr2018

Reference: CS\_WI\_BS005

- f. Medical or scientific judgement should be exercised in deciding whether reporting is appropriate in other situations, such as important medical events that may not be immediately life-threatening or result in death or hospitalization but may jeopardize the patient or may require medical or surgical intervention to prevent one of the other outcomes listed in the above definition. These should also be considered serious. Examples of such events are invasive or malignant cancers, intensive treatment in an emergency room or at home for allergic bronchospasm, blood dyscrasias or convulsions that do not result in hospitalization, or development of drug dependency or drug abuse.
- g. All events of possible drug-induced liver injury with hyperbilirubinaemia defined as ALT  $\geq$  3xULN and bilirubin  $\geq$  2xULN ( $>35\%$  direct) (or ALT  $\geq$  3xULN and INR  $>1.5$ , if INR measured) termed 'Hy's Law' events (INR measurement is not required and the threshold value stated will not apply to patients receiving anticoagulants).

On the Adverse Events page of the eCRF, serious adverse events are those events respond as "Yes" for item "Serious Criteria".

Summaries of all serious TEAEs and serious TEAEs Related to study medication in treatment phase by SOC and PT for each SHR0302 dose level, placebo and overall will be prepared. All serious TEAEs and serious TEAEs related to study medication will also be summarized similarly for 8 mg QD total, 4 mg BD total, 4 mg QD total, Placebo only and overall during the whole study period. Patients with missing relationship will be treated as probably related.

Listings will include all SAEs (serious TEAEs and serious Non-TEAEs). Listings for SAEs will include the start date, end date, severity, severity, relationship to study drug, action taken, outcome, SAE criteria, and a liver event or not, etc.

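### Protocol 7.3.10 requires every pregnancy to be followed to outcome, then lets placebo subjects go unfollowed, so active pregnancy follow-up depends on the arm and can signal allocation (low severity)

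*Protocol*

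**What the plan says.** Protocol 7.3.10 opens with a rule that names no arm. Any pregnancy after the first dose goes on a pregnancy form and is reported within 24 hours. It makes follow-up to outcome mandatory for each pregnancy, and on duration it says: "status of mother and the newborn should be followed up to 1 month after birth". Complications and medically indicated terminations are AEs or SAEs, and a later paragraph makes spontaneous abortion an SAE. Partner pregnancies of male subjects are also recorded, with the partner's authorization. On blinding, the section says: "Pregnancies will remain blinded to the study team".

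The next paragraph deals with the subject's right to know her treatment. If she chooses to "receive unblinded treatment information, the individual blind should be broken by the investigator". The sentence that follows is the exemption: "Subjects randomized to placebo need not be followed in the treatment phase". This is current text, and no other section limits or withdraws it.

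Three other places bear on the point:
- Protocol 7.3.14 collects AEs to the follow-up contact and SAEs from consent to any follow-up contact, in all arms.
- Protocol 9.3.4.4 lists pregnancy data only, and SAP 16.7 lists pregnancy tests.
- SAP 16.1.4 plans these tables: "Summaries of all serious TEAEs and serious TEAEs Related to study medication in treatment phase by SOC and PT for each SHR0302 dose level, placebo".

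**The concern.** Harms can be compared between arms only if they are looked for in the same way. Under the exemption, a pregnancy on any SHR0302 dose must be pursued to outcome and to 1 month after birth, while one on placebo may be left after the initial report. If a late loss or a neonatal finding then came to light on an active dose, there would be no equally followed placebo pregnancy to set beside it. The protocol requires highly effective contraception, so such an event would be read closely.

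The second issue is blinding. Someone must know the arm to decide that a subject is exempt, and the decision to stop is itself informative.

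**Working it through.** No figure in the plan needs reproducing. The check is a comparison of the passages, followed by a rough estimate of frequency.

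**1. Follow-up duties in 7.3.10 and 7.3.14, by arm**

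| Duty | Active doses | Placebo, treatment phase |
|---|---|---|
| Pregnancy form, report within 24 hours | required | required |
| Complications and medical terminations as AE/SAE | required | required |
| Spontaneous abortion as SAE | required | required |
| Routine AE/SAE collection to the follow-up contact | required | required |
| Active follow-up to outcome, and of the newborn to 1 month | required | required by the general rule, optional under the exemption |

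Only the last row differs by arm, and it is the row on which the section contradicts itself.

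**2. Scope of the exemption**

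The phrase about the treatment phase has two readings. It may mean pregnancies that arise in weeks 0 to 8, in which case all later follow-up of those pregnancies becomes optional. Or it may mean follow-up carried out in weeks 0 to 8, in which case less is lost. The text does not decide, and either reading conflicts with the general rule.

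**3. Blinding**

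- If the exemption covers every pregnancy, the code must be opened each time to learn who is exempt. Section 6.3 lets the investigator unblind only in an emergency, and 7.3.10 adds only the subject's own choice.
- If it covers only subjects who chose to be unblinded, no further unblinding is needed. Stopping follow-up still tells the study team that the subject was on placebo, and continuing suggests active drug.

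**4. Frequency (assumed inputs)**

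From the documents: 152 subjects randomized 1:1:1:1, so 152 / 4 = 38 on placebo; treatment phase 8 weeks = 8 / 52.18 = 0.153 years. The documents give no sex mix, childbearing share or pregnancy rate, so these are assumptions.

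Expected placebo pregnancies E = 38 × proportion women × proportion of childbearing potential × 0.153 × rate per woman-year. Chance of at least one = 1 − exp(−E).

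| Scenario | Women | Childbearing potential | Rate per woman-year | E | Chance of at least one |
|---|---|---|---|---|---|
| Low | 0.35 | 0.6 | 0.01 | 0.012 | 1.2% |
| Middle | 0.50 | 0.7 | 0.03 | 0.061 | 5.9% |
| High | 0.60 | 0.8 | 0.06 | 0.168 | 15.5% |

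The three active arms together have three times E over the same 8 weeks: 0.037, 0.18 and 0.50. Partner pregnancies are not counted, so these figures are not an upper bound for everything 7.3.10 covers.

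**The case against.** The other side has a good case on size.

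- **The wording is permissive.** It lifts a duty to follow and does not bar collection. A reader might infer that the placebo count is zero by rule, or that an ordinary miscarriage would appear as an SAE on drug only. The documents do not support either inference: a known placebo miscarriage must also be reported as an SAE.
- **Protocol 7.3.14 is not shown to conflict.** Its rule, cut here before its last word, reads: "All SAEs will be followed up until resolution, until the condition stabilizes, until the event is otherwise explained, or until the subject is lost to". A placebo SAE, once reported, still falls under it. The gap concerns events that nobody learns of because nobody asked.
- **The tables are little affected.** Pregnancy data are listed only, and SAP section 16 plans no statistical comparison of safety data unless otherwise specified. SAP Appendix 2 assigns an event to the treatment phase only if it starts before the week 8 visit. Birth outcomes come months later and would not enter the treatment-phase table in any arm.
- **Unblinding does limited harm.** The sentence follows directly on the subject's right to be unblinded and may be meant only for that case. The pregnant subject is already withdrawn and off study drug, so few blinded assessments remain. Section 6.3 also lets sponsor or CRO staff unblind any subject with an SAE.

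All of this stands, and it lowers the severity. It does not remove the contradiction within 7.3.10. It also leaves active follow-up to outcome mandatory on SHR0302 and optional on placebo, and leaves the study-team blinding statement at odds with a rule that acts on allocation.

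**Conclusion.** The point holds, at low severity. Section 7.3.10 gives two incompatible follow-up rules. If the exemption is used, mandatory pursuit of later pregnancy outcome and newborn status depends on the arm, and stopping it signals placebo.

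The textual finding needs no assumption. The size does: about 0.01 to 0.17 expected placebo-subject pregnancies in 8 weeks, a chance of roughly 1% to 15% of at least one, on assumed rates and without partner pregnancies. At such counts no between-arm inference on pregnancy outcome would be possible even with equal follow-up. The reason to act is consistent ascertainment and a protocol that sites can follow. The primary endpoint, alpha and power are not affected.

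**What to change.** Reconcile the passages in 7.3.10 by deleting the placebo exemption and stating, for example: *Pregnancy outcome, pregnancy complications and newborn status to 1 month after birth are collected in the same way in every arm, without reference to treatment assignment.*

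The withdrawal rule and the subject's right to her treatment information stay as they are; the change concerns outcome data collection only. It also removes the ambiguity about the treatment phase and any need to consult the code to decide on follow-up.

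The cost is a one-sentence amendment and, at most, a very few additional pregnancies followed with the existing form, including partner pregnancies where authorized. No extra subjects, study visits or assays are needed.
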